APPENDIX F
SOP for Investigator INDs Held by Physician
Members of the UAB Comprehensive Cancer Center
(available upon request)

APPENDIX G

Prohibited Medications

Drug Class	Agent	Washout ¹
CYP3A4 Inducers		
Antibiotics	All rifamycin class agents (e.g. rifampicin, rifabutin, rifapentine)	14 days
Anticonvulsants	Phenytoin, carbamazepine, barbiturates (e.g. phenobarbital)	
Antiretrovirals	Efavirenz, nevirapine, tipranavir, etravirine	
Glucocorticoids (oral)	Cortisone (>50 mg), Hydrocortisone (>40 mg), prednisone (>10 mg), methylprednisolone or triamcinolone (>8 mg), betamethasone or dexamethasone (>1.5 mg) ²	
Other	St. John's Wort, modafinil	

CYP3A4 Inhibitors		
Antibiotics	Clarithromycin, erythromycin, troleandomycin	7 days
Antifungals	Ketoconazole, itraconazole, fluconazole (>150 mg daily), voriconazole	
Antiretrovirals, Protease Inhibitors	Delavirdine, nelfinavir, amprenavir, ritonavir, indinavir, saquinavir, lopinavir, atazanavir	
Calcium channel blockers	Verapamil, diltiazem	
Antidepressants	Nefazodone, fluvoxamine	
GI Agents	Cimetidine, aprepitant	
Fruits/fruit juices	Grapefruit, star fruit, and papaw	
Other	Amiodarone	6 months

Miscellaneous		
Antacids	Mylanta, Maalox, Tums, Rennies	1 hr before/after dosing
Herbal/dietary supplements³	Ginkgo biloba, kava, grape seed, valerian, ginseng, echinacea, evening primrose oil	14 days

1. At the time of screening, if a subject is receiving any of the above listed medications/substances, the medication or substance must be discontinued (if clinically appropriate) for the period of time specified prior to administration of the first dose of lapatinib and throughout the study period in order for the subject to be eligible to participate in the study.
2. Glucocorticoid daily doses (oral) \leq 1.5 mg dexamethasone are allowed. Glucocorticoid conversions are provided in parentheses.
3. Because the composition, pharmacokinetics, and metabolism of many herbal supplements are unknown, the concurrent use of all herbal supplements is strongly discouraged during the study.

APPENDIX H

Suggested Management of Dermatological Toxicities

For all patients: advise patients to use acne cleanser twice daily (face, chest, and neck), apply alcohol-free moisturizer twice daily (e.g. Cetaphil), and use sunscreen with SPF 15 or higher.

Rash Severity

1. **Mild:** Generally localized, minimal symptoms, no impact on ADL

Intervention:

- Maintain dose & monitor for change in severity
- No Treatment OR topical Clindagel 1% BID

Reassess after 1-2 weeks; if symptoms worsen or fail to improve, proceed to next step

2. **Moderate:** Generalized, mild symptoms (e.g. pruritus/tenderness), minimal impact on ADL

Intervention:

- Maintain dose & monitor for change in severity
- Topical Clindagel 1% BID plus minocycline 100 mg BID or Doxycycline 100 mg BID

Reassess after 1-2 weeks; if symptoms worsen or fail to improve, proceed to next step

3. **Severe:** Generalized, severe symptoms (e.g. pruritus, tenderness), significant impact on ADL

Intervention:

- Consider drug holiday; continue treating as below:
- Topical Clindagel 1% BID plus minocycline 100 mg BID or doxycycline 100 mg BID plus Medrol Dose-Pak

Reassess after 1-2 weeks; if symptoms worsen or fail to improve, consider dose reduction

APPENDIX I

Diarrhea Management Guidelines

Diarrhea Management Guidelines

Background

Experience thus far suggests that when lapatinib is used as monotherapy 51% of patients experience diarrhea; most diarrhea presents as uncomplicated NCI CTCAE Grade 1 or 2 (G1 30%, G2 15%, G3 6%, G4<1%) (Crown, 2008).

In rare cases, diarrhea can be debilitating, and potentially life threatening if accompanied by dehydration, renal insufficiency, and/or electrolyte imbalances.

Standardized and universal guidelines have been developed by an American Society of Clinical Oncology (ASCO) panel for treating chemotherapy-induced diarrhea (Benson, 2004). Presented in the sections below are the recommended guidelines for the management of diarrhea in subjects receiving lapatinib-based therapy; these guidelines were derived from the recommendations published by the ASCO panel (Benson, 2004).

Early identification and intervention is critical for the optimal management of diarrhea. A subject's baseline bowel patterns should be established so that changes in patterns can be identified while subject is on treatment.

It is strongly recommended to give subjects receiving lapatinib-based therapy a prescription of loperamide with instructions to start loperamide at the onset of diarrhea as per the recommendations outlined below. Subjects should be instructed to first notify their physician/healthcare provider at onset of diarrhea of any severity.

An assessment of frequency, consistency and duration as well as knowledge of other symptoms such as fever, cramping, pain, nausea, vomiting, dizziness and thirst should be taken at baseline. Consequently subjects at high risk of diarrhea can be identified. Subjects should be educated on signs and symptoms of diarrhea with instructions to report any changes in bowel patterns to the physician.

It is recommended that subjects keep a diary and record the number of diarrhea episodes and its characteristics. They should also include information on any dietary changes or other observations that may be useful in the evaluation of their diarrhea history.

If subjects present with diarrhea of any Grade, check they are taking lapatinib correctly, i.e. single daily dose, rather than splitting it through the day. Obtain information on food (solid and liquid) and over the counter (OTC) medication, including herbal supplements, taken during the lapatinib treatment period.

Definitions

National Cancer Institute (NCI) guidelines define diarrhea compared to baseline (Table 1).

Table 1: NCI Common Terminology Criteria for Grading Diarrhea Adverse Events¹

Adverse Event Grade	Diarrhea
1	Increase of <4 stools/day over baseline; mild increase in ostomy output compared to baseline
2	Increase of 4-6 stools/day over baseline; moderate increase in ostomy output compared to baseline;
3	Increase of ≥ 7 stools/day over baseline; incontinence; hospitalization indicated; severe increase in ostomy output compared to baseline; limiting self care activities of daily living (ADL)
4	Life-threatening consequences; urgent intervention indicated
5	Death

¹ National Cancer Institute Common Terminology Criteria for Adverse Events (CTCAE) Version 4.0

Uncomplicated diarrhea is considered mild-to-moderate and defined as CTCAE Grade 1 or 2 with no complicating signs or symptoms.

Complicated diarrhea is severe and defined as any CTCAE Grade 3 or 4 diarrhea, or Grade 1 or 2 with one or more of the following signs or symptoms:

- Moderate to severe abdominal cramping
- Nausea/vomiting \geq Grade2
- Decreased performance status
- Fever
- Sepsis
- Neutropenia
- Frank bleeding (red blood in stool)
- Dehydration

Management Guidelines for Subjects Receiving Lapatinib Alone or as Combination**A) Uncomplicated Diarrhea****I. CTCAE Grade 1**

NOTE: Subject should be instructed to: start supportive care immediately at the first episode of diarrhea (i.e., unformed stool) and call their physician.

1. Administer loperamide*
 - a. Initial dose 4mg followed by 2mg after every unformed stool. Re-evaluate after 24 hours, if:
 - i. Diarrhea is resolving:
 - Continue loperamide treatment at 2mg dose after every unformed stool until diarrhea free (i.e., <Grade 1/bowel patterns returned to baseline) for 12 hours.
 - If diarrhea recurs, re-initiate loperamide treatment as needed to maintain normal bowel patterns
 - ii. Diarrhea is not resolving:
 - Administer loperamide at 2mg every 4 hours for the next 24 hour. Re-evaluate after 24 hours. If diarrhea is resolving, administer loperamide at 2mg after every unformed stool until diarrhea free (i.e., <Grade 1/bowel patterns returned to baseline) for 12 hours. If diarrhea is not resolving continue loperamide treatment at 2mg every 4 hours and re-evaluate every 24 hours.
 - b. If Grade 1 diarrhea persists for more than 1 week with loperamide treatment, consider treatment with second-line agents (i.e., octreotide, budesonide or tincture of opium).
 2. Dietary modifications which are essential in the management of diarrhea include the following recommendations (American Cancer Society; National Cancer Institute):
 - a. Stop all lactose containing products and eat small meals
 - b. Avoid spicy, fried and fatty foods, raw vegetables and other foods high in fiber
 - Eat foods low in fiber (i.e., lean meat, rice, skinless chicken or turkey, fish, eggs, canned or cooked skinless fruits, cooked/pureed vegetables)
 - c. Avoid caffeine and alcohol as they can irritate the bowel and increase motility
 - d. Hydration: Drink 8-10 large glasses of clear liquids a day (e.g., water, electrolyte drink).
 - Avoid acidic drinks such as tomato juice and fizzy soft drinks
 - e. Supplement diet to include foods rich in potassium (e.g., bananas, potatoes, and apricots), evaluate their impact on diarrhea due to the fiber content (e.g., apricots)
 3. Continue with study treatment (i.e., lapatinib-based treatment)

Continue with supportive care until diarrhea has resolved (diarrhea free for 12 hours/bowel pattern return to baseline). Once diarrhea has resolved, the subject can begin to gradually re-introduce foods from their normal diet. If diarrhea recurs following stopping of loperamide treatment, resume loperamide treatment at the dose and schedule recommended above and re-introduce diet modifications. Continue with study treatment. If Grade 1 diarrhea persists for ≥ 2 weeks, refer to the management guidelines for Persistent Grade 2 Diarrhea.

II. CTCAE Grade 2

NOTE: Subject should be instructed to call physician at first episode of diarrhea and start supportive care immediately

1. Administer loperamide*
 - a. Initial dose 4mg followed by 2mg every 4 hours or after every unformed stool. Re-evaluate after 24 hours. If:
 - i. Diarrhea is resolving, continue loperamide treatment at 2mg dose after every unformed stool until diarrhea free (i.e., <Grade 1/bowel patterns returned to baseline) for 12 hours
 - o If diarrhea recurs, re-initiate loperamide treatment as needed to maintain normal bowel patterns
 - ii. Diarrhea is not resolving, consider loperamide dose of 2mg every 2 hours for 24 hours. If Grade 2 diarrhea persists after total of 48 hours of loperamide treatment, start second-line agents (i.e., octreotide, budesonide or tincture of opium).
 - o Consider performing stool work-up, CBC, electrolytes and other tests as appropriate
2. Dietary modifications which are essential in the management of diarrhea include the following recommendations (American Cancer Society; National Cancer Institute):
 - a. Stop all lactose containing products and eat small meals
 - b. Avoid spicy, fried and fatty foods, bran, raw vegetables and other foods high in fiber
 - Eat foods low in fiber (i.e., lean meat, rice, skinless chicken or turkey, fish, eggs, canned or cooked skinless fruits, cooked/pureed vegetables)
 - c. Avoid caffeine and alcohol as they can irritate the bowel and increase motility
 - d. Hydration: Drink 8-10 large glasses of clear liquids a day (e.g., water, electrolyte drink).
 - Avoid acidic drinks such as tomato juice and fizzy soft drinks
 - e. Supplement diet to include foods rich in potassium (e.g., bananas, potatoes, and apricots), evaluate their impact on diarrhea due to the fiber content (e.g., apricots)
3. Continue with study treatment (i.e., lapatinib-based treatment)

Continue with supportive care until diarrhea has resolved (diarrhea free for 12 hours/bowel pattern return to baseline). Once diarrhea has resolved, the subject can begin to gradually re-introduce foods from their normal diet. Refer to Section IV “Recurrent Diarrhea” for study treatment guidelines. If diarrhea recurs following stopping of loperamide treatment, resume loperamide treatment at the dose and schedule recommended above and re-introduce diet modifications.

III. Persistent (\geq 3 days/72 hours) Grade 2 Diarrhea: hold lapatinib and chemotherapy (if applicable) until diarrhea resolves (<Grade 1/return to baseline bowel pattern).

1. If supportive care measures and the interruption of study treatment (i.e., lapatinib and if applicable chemotherapy) are ineffective in treating persistent Grade 1 or Grade 2 diarrhea, perform stool work-up, CBC, electrolytes and other tests as appropriate, consider consulting with a gastrointestinal (GI) specialist.
 - a. After diarrhea resolves (<Grade 1/return to baseline bowel pattern), resume treatment with lapatinib and chemotherapy (if applicable).

IV. Recurrent Diarrhea (more than 1 occurrence of Grade 2 diarrhea): once the 2nd occurrence of Grade 2 diarrhea resolves to \leq Grade 1, consider reducing the dose of lapatinib by 250mg or 1 tablet, unless the lapatinib dose already had been reduced to 750mg. No further dose reduction is recommended for subjects taking lapatinib at 750mg.

2. Consider a dose reduction for chemotherapy (if applicable)

B) Complicated Diarrhea

I. CTCAE Grade 3 or Grade 1 or 2 with complicating features (severe cramping, severe nausea/vomiting, decreased performance status, fever, sepsis, Grade 3 or 4 neutropenia, frank bleeding, dehydration)

1. Subject **must** call physician immediately for any complicated severe diarrhea event
2. If loperamide has not been initiated, initiate loperamide immediately: Initial dose 4mg followed by 2mg every 2 hours or after every unformed stool*
3. Refer to the dietary modification recommendations for Grade 1 and Grade 2 uncomplicated diarrhea
4. For dehydration use intravenous fluids as appropriate, if subject presents with severe dehydration administer octreotide
5. Perform stool work-up, CBC, electrolytes and other tests as appropriate
6. Administer antibiotics as needed (example fluoroquinolones), especially if diarrhea is persistent beyond 24 hours or there is fever or Grade 3-4 neutropenia

Hold lapatinib and chemotherapy (if applicable) until symptoms resolve to \leq Grade 1 (without complicating features) and reintroduce lapatinib at a reduced dose (unless dose had been reduced to 750mg, contact *medical monitor for further guidance*): **INFO:** FOR ISS: remove the italicized guidance

[figure not shown]
7. Supportive care and other interventions should be continued until diarrhea free (i.e., <Grade 1/bowel patterns returned to baseline) for 24 hours
8. Intervention may require hospitalization for subjects most at risk for life threatening complications

II.CTCAE Grade 4

1. Subject must call physician immediately for any Grade 4 diarrhea event
2. Hold treatment with lapatinib, hold chemotherapy or other concurrent anticancer therapy (if applicable)
 - Contact the Medical Monitor to discuss the patient case history and the possibility of re-initiation of study treatment, including dose modifications, following resolution of diarrhea (\leq Grade 1)
- (*INFO: NOTE: Can Modify Figure 1Grade 4 with this guidance; For Investigator sponsored studies substitute the above recommendation with the following:* Evaluate the patient case history when deciding on the re-initiation of study treatment, including dose modifications, following resolution of diarrhea (\leq Grade 1))
3. If loperamide has not been initiated, initiate loperamide immediately: Initial dose 4mg followed by 2mg every 2 hours or after every unformed stool*
4. For dehydration use intravenous fluids as appropriate, if subject presents with severe dehydration administer octreotide
5. Perform stool work-up, CBC, electrolyte and other tests as appropriate
6. Recommend consulting with GI specialist
7. Administer antibiotics as needed (example fluoroquinolones), especially if diarrhea is persistent beyond 24 hours or there is fever or Grade 3/4 neutropenia
8. Supportive care and other intervention should be continued until diarrhea free (i.e., $<$ Grade 1/bowel patterns returned to baseline) for 24 hours
9. Intervention may require hospitalization for subjects most at risk for life threatening complications

*It is recommended that the maximum cumulative daily dose of loperamide follows local guidance Refer to and follow the recommended supportive care guidelines in the previous sections and as depicted in Figure 1.

Figure 1: Algorithm for the management of diarrhea in subjects treated with lapatinib-based therapy

1. For Grade 1 diarrhea that persists for 2 weeks or longer, refer to Section III
2. For Grade 2 diarrhea that persists longer than 3 days/72 hours, refer to Uncomplicated Diarrhea Section III
3. For recurrent diarrhea, refer to Uncomplicated Diarrhea Section IV for further management guidelines

References

American Cancer Society. Coping with physical and emotional changes: Diarrhea: what the subject can do. Diahttp://www.cancer.org/docroot/MBC/content/MBC_2_3X_Diarrhea.asp

Benson A, Jaffer AA, Catalano RB, et al. Recommended Guidelines for the Treatment of Cancer

Treatment-Induced Diarrhea. Journal of Clinical Oncology 2004; 22:2918-2926.

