3.0 STUDY DESIGN (Table 1 and Figure 7)

The study is an open-label, single arm, single institution, pilot clinical trial of Veliparib (a PARP inhibitor) in combination with Lapatinib (an EGFR inhibitor) in patients with pathologically confirmed TNBC (ER negative, PR negative, HER-2-Neu negative by IHC [0, 1] or FISH) who have not received prior therapy in the metastatic setting (but failed anthracyclines and taxanes in the

neoadjuvant or adjuvant setting) or who have failed prior chemotherapy in the metastatic setting (including anthracyclines and taxanes and no more than two prior regimens for metastatic disease as long as patients have adequate performance status – see Appendix B). The data obtained in this pilot study will be used to design a phase II clinical trial that will be conducted by the Translation Breast Cancer Research Consortium.

As described in **Figure 7**, patients will receive Lapatinib (1250 mg PO daily continuously) in combination with Veliparib (200 mg PO every 12 hours continuously). A cycle of therapy is defined as 28 days of PO therapy. Lapatinib will start Day 1 cycle 1 and Veliparib will start on Day 2 Cycle 1 (for better understanding of the PK of the drugs as well as to induce a DSB repair defect first with Lapatinib). Dose reductions of Lapatinib and Veliparib will be allowed. Patients developing grade 1 and 2 toxicities will be permitted to take a drug holiday of up to 14 days; after the drug holiday, if the adverse event has resolved to the satisfaction of the investigator, the study drugs may be resumed at the same level. In the event of recurrent toxicity, there will be two dose reductions permitted (dose reduction minus one will be Lapatinib 1000 mg PO daily continuously and Veliparib 150 mg PO every 12 hours continuously); dose reduction minus two will be Lapatinib 750 mg PO daily and Veliparib 100 mg PO every 12 hours continuously. If the adverse event recurs after dose reduction two, the patient will be taken off the study. Patients developing grade 3 and 4 toxicities will be interrupted for up to 14 days; after the drug holiday, if the adverse event has resolved to the satisfaction of the investigator, the study drugs may be resumed at a reduced dose (Lapatinib 1000 mg PO daily continuously and Veliparib 150 mg PO every 12 hours continuously). If the adverse event recurs, the patient will be taken off the study.

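### The 3-week LVEF restart window conflicts with the 2-week removal rule, and Appendix I's lapatinib-only diarrhea steps are not tied to the hold and removal rules in 3.0 (wrong as written, minor)

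*Combined protocol and SAP*

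**What the plan says.** **LVEF.** Under 6.2.3, repeated in footnote 8 of 6.6, a confirmed relative fall of at least 20% to below the institutional limit stops lapatinib temporarily. If LVEF recovers within the following 3 weeks, the patient may restart at a reduced dose. Section 6.2.4 takes patients off treatment once a delay exceeds 2 weeks and makes no LVEF exception. Section 5.2.3 limits a lapatinib holiday to 14 days at every toxicity grade.

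**Diarrhea, body text.** In 3.0, "Patients developing grade 3 and 4 toxicities will be interrupted for up to 14 days", after which both drugs may restart together at lapatinib 1000 mg daily and veliparib 150 mg every 12 hours. If the grade 3-4 event recurs, the patient leaves the study. For grade 1-2 events the holiday is also at most 14 days, restart may be at the same level, and recurrence permits two paired reductions before removal. Section 5.1.5 applies the same interruption and reduction to veliparib by name.

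**Diarrhea, Appendix I.** Section 5.2.2 refers the reader to this appendix, which calls itself "recommended guidelines for the management of diarrhea in subjects receiving lapatinib-based therapy".
- Persistent grade 2: "hold lapatinib and chemotherapy (if applicable) until diarrhea resolves".
- Recurrent grade 2: "consider reducing the dose of lapatinib by 250mg or 1 tablet".
- The complicated-diarrhea step covers "CTCAE Grade 3 or Grade 1 or 2 with complicating features". It reads "Hold lapatinib and chemotherapy (if applicable) until symptoms resolve to" grade 1 or lower, "and reintroduce lapatinib at a reduced dose (unless dose had been reduced to 750mg, contact" the medical monitor.

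**The concern.** Two parts of one protocol give a site different instructions for the same patient. On LVEF, one section permits a restart in a week when another requires the patient to come off treatment. On diarrhea, the appendix describes what is interrupted as "the interruption of study treatment (i.e., lapatinib and if applicable chemotherapy"; section 6.2 bars concomitant chemotherapy, so in practice only lapatinib is named.

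The primary objective is safety and treatment tolerance, and the results are meant to inform a phase II design. Whether a patient is recorded as removed for toxicity, and how long a hold may last, are part of the tolerance record. They should not depend on which page the site follows.

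**Working it through.** The plan states no figure to reproduce. The check sets the rules side by side, with simple arithmetic on size.

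**LVEF**
1. Restart window (6.2.3, 6.6 footnote 8): 3 weeks = 21 days.
2. Removal rule (6.2.4) and lapatinib holiday cap (5.2.3): 14 days.
3. Overlap: 21 − 14 = 7 days. Recovery on days 15 to 21 permits restart under 6.2.3 and requires removal under 6.2.4.
4. Size, taking the 1.4% incidence in 2.6: 20 × 0.014 = 0.28 patients expected; chance of at least one = 1 − 0.986^20 = 0.25. Only confirmed falls below grade 3 that recover in that one week are affected, so the range is 0 to about 0.28.

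**Diarrhea**

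| Event | 3.0, with 5.1.5 for veliparib | Appendix I text | Difference |
|---|---|---|---|
| First persistent grade 2 | Holiday up to 14 days; same level may resume | Hold lapatinib, then resume | Which drug is held, and the cap; no reduction on either side |
| Recurrent grade 2 | Paired reductions permitted: 1000/150, then 750/100 | Consider 250 mg less lapatinib | Lapatinib agrees (1250 − 250 = 1000); veliparib not named |
| First grade 3 | Interrupt up to 14 days; restart at 1000/150 | Hold lapatinib; restart it reduced | Veliparib not named; no cap |
| Repeat grade 3 | Off study | Not addressed expressly; the same step would restart lapatinib unless already at 750 mg | Removal |
| Grade 1-2 with complicating features | May resume at same level | Restart lapatinib reduced | None binding: 3.0 is permissive |

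Appendix I's Figure 1 is not shown, so the absence of a cap or off-study point is established for its text only. Grade 4 is outside this point, because that step also reaches other concurrent anticancer therapy.

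Size, assuming the lapatinib monotherapy rates carry over to the combination, for which the documents give no rates:
- Grade 3 at 6% (Appendix I): 20 × 0.06 = 1.2 patients; chance of at least one = 1 − 0.94^20 = 0.71.
- Grade 3 at the under-10% bound (5.2.2): below 20 × 0.10 = 2.0 patients; chance below 1 − 0.90^20 = 0.88.
- Grade 2 at 15% (Appendix I): 20 × 0.15 = 3.0 patients, of whom an unknown part persists or recurs.

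The grade 3 figures are first events. The removal conflict needs a repeat grade 3 event, whose frequency the documents do not give.

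**Restart dose in 5.2.3**

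The grade 3-4 restart is written as 1000 mg every 12 hours: 2 × 1000 = 2000 mg/day. Since 2000 / 1250 = 1.6, this is 60% above the starting dose although it is called a reduction. Section 3.0 gives 1000 mg daily.

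**The case against.** Appendix I is a generic lapatinib template: it offers recommendations, and template notes for investigator-sponsored studies are still in its text. It nowhere says that veliparib continues during a hold. The body text places dose changes in the earlier sections: 3.0 speaks of adjusting both drugs as set out there, and 6.7.6 points back to earlier text. A site can apply 5.1.5 and the 14-day cap alongside Appendix I without breaching either. Most of this stands. What remains is that those pointers do not rank the rules, 5.2.2 sends the reader to the appendix, and its grade 3 step is worded as an instruction.

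On LVEF, 6.2.3 is the specific rule and 6.2.4 the general one. Section 4.3 also counts its 2 weeks from the planned next cycle. With an echocardiogram on day 1 and the repeat 1 to 2 weeks later, the hold starts about day 8 to 15. Twenty-one days then ends about day 29 to 36, at most about 7 days into the next 28-day cycle and inside the limit in 4.3. That defence holds for 4.3 on that timing. It does not remove the conflict with 6.2.4 or with the cap in 5.2.3. One could argue that a lapatinib-only hold is not a treatment delay, but 6.2.4 does not say so.

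**Conclusion.** Wrong as written, and minor. The LVEF conflict is direct but rare: at most about 0.28 of 20 patients, if the 1.4% lapatinib incidence applies to this combination and population. The diarrhea problem is a missing link between Appendix I and 3.0. It leaves the hold cap, and removal after a repeat grade 3 event, open to two readings. The 5.2.3 restart dose disagrees with 3.0 outright.

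The documents do not support several stronger readings that a reader might infer:
- **Veliparib stays at full dose.** One could compute 2 × 200 = 400 against 2 × 150 = 300 mg/day after a first grade 3 event, or 14 × 400 = 5,600 mg taken over a full 14-day lapatinib-only hold. These arise only if 5.1.5 is ignored.
- **Appendix I conflicts with paired reduction for a first persistent grade 2 event.** Neither source reduces there.
- **The grade 3 diarrhea toxicity count is distorted.** Grade 3 diarrhea counts as a toxicity whichever rule is followed.
- **Veliparib ought to be held for an LVEF fall.** The plan gives no basis for this, and 5.2.2 attributes the decline to lapatinib.

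**What to change.** - **LVEF:** either write the 3-week window into 6.2.4 and 5.2.3 as an explicit exception, or shorten it to 2 weeks in 6.2.3 and footnote 8 of 6.6. If the exception is chosen, repeat it in 3.0, which carries the same 14-day cap.
- **Diarrhea:** state in 5.2.2 and Appendix I that 3.0, including its Cohort -1 rules, governs holds, paired reductions, the 14-day cap and removal for both drugs, and that Appendix I governs supportive care.
- **5.2.3:** change the grade 3-4 restart from 1000 mg every 12 hours to 1000 mg daily, to match 3.0.

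The cost is a wording amendment and its IRB review. Sample size, visits and analyses do not change.
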